9.2.2 Sensitivity Analysis

The potential confounding effect of change in NSAID/acetaminophen usage on the treatment effect will be considered for sensitivity analysis, details of which can be found in [Section 12.3](#). Missing data will be imputed using the MI method for additional sensitivity analysis. The main primary analysis will also be repeated for subjects in the PPAS.

9.3 Secondary Efficacy Analysis

9.3.1 Main Analysis

Change over time in secondary endpoints will be characterized using MMRM to estimate change from baseline with treatment group, week, treatment \times week interaction and baseline value as covariates. The model will include all timepoints for subjects in the FAS and will be evaluated for Pain NRS at Week 24 and WOMAC Function and Patient Global Assessment at Weeks 12 and 24.

9.3.2 Sensitivity Analysis

The potential confounding effect of change in NSAID/acetaminophen usage on the treatment effect will be considered for sensitivity analysis, details of which can be found in [Section 12.3](#). Missing data will be imputed using the MI method for additional sensitivity analysis. The main secondary analyses will also be repeated for subjects in the PPAS.

9.4 Other Efficacy Analysis

Change over time in WOMAC Pain and WOMAC Total scores will be characterized using a MMRM to estimate change from baseline with treatment group, week, treatment \times week interaction and baseline value as covariates. The model will include all timepoints, but will be evaluated at Weeks 12, and 24. Unadjusted 95% confidence intervals and P values will be reported.

The number and percent of subjects reporting Patient Acceptable Symptom State (PASS), 30% improvement, 50% improvement, and 70% improvement in Pain NRS, WOMAC Function, and

Patient Global Assessment will be summarized. PASS is defined as a reported value of less than or equal to 30 on a 0-100 scale. Logistic regression analysis will be implemented for improvement in these assessments as well, with 95% confidence intervals and P values reported.

The analyses described above will be performed on subjects in the FAS.

10. SAFETY AND TOLERABILITY ANALYSIS

The analysis of safety outcome measures will be performed on the Safety Analysis Set. No formal statistical tests are planned for safety.

10.1 Adverse Events

All AEs collected in this study are treatment emergent events that occur during the course of the study that are not present prior to Day 1 study medication injection, or, if present at the time of study medication injection, have worsened in severity during the course of the study. AEs will be presented in summary tables depicting the number and percent of unique subjects experiencing each AE and the number of AEs overall and within each treatment group. The following summaries will be provided:

- All AEs and all SAEs by severity and relationship to study product
- AEs by highest degree of seriousness, severity, and relationship to study drug
- AEs by MedDRA system organ class and preferred term
- AEs with incidence of greater than 2% in the active treatment group sorted by preferred term incidence
- Target-knee-related AEs and SAEs sorted by preferred term incidence
- AEs leading to study withdrawal
- SAEs in subjects diagnosed with COVID-19

Separate subject-level listings will be provided for all AEs and all SAEs.

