4.2 Method of Treatment Assignment and Randomization

Subjects were randomized 1:1 (0.07 mg active per 2 mL injection:2 mL placebo) to each treatment group using Medidata Rave Randomization and Trial Supply Management (RTSM) with a permuted block design stratified by study site. 250 blocks of size 6 were generated for a total of 1500 possible subject slots.

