5. SAMPLE SIZE DETERMINATION

A sample size of approximately 725 subjects was initially selected for this study to yield 325 evaluable subjects per treatment group assuming 10% dropout.

One thousand Monte Carlo simulations generated baseline and follow-up data from a bivariate normal distribution for each treatment group and estimated the least squares difference between treatment and placebo in an outcome's change using a baseline-adjusted analysis of covariance (ANCOVA). The proportion of statistically significant results at $\alpha = 0.05$ was estimated as the approximate power for a sample size of 325 subjects per group.

The following assumptions were made based upon observed data in the Phase 2 dose-ranging studies (SM04690-OA-02 and SM04690-OA-04):

- For Pain NRS, assuming a baseline mean (standard deviation [SD]) of 6.0 (1.5), follow-up mean (SD) of 3.0 (3.0) for SM04690 and 3.8 (3.0) for placebo (presumed treatment difference -0.8), and a baseline to follow-up correlation of 0.25, power is estimated to be 93.5%.
- For WOMAC Function, assuming a baseline mean (SD) of 60 (14), follow-up mean (SD) of 30 (29) for SM04690 and 37.5 (29) for placebo (presumed treatment difference -7.5), and a baseline to follow-up correlation of 0.25, power is estimated to be 92.0%.
- For Patient Global Assessment, assuming a baseline mean (SD) of 55 (20), follow-up mean (SD) of 35 (27) for SM04690 and 42.5 (27) for placebo (presumed treatment

difference -7.5), and a baseline to follow-up correlation of 0.25, power is estimated to be 95.3%.

Based upon a blinded evaluation of aggregate data, sample size assumptions were reassessed, and additional Monte Carlo simulations generated. A sample size of approximately 500 subjects was re-estimated for this study to yield 225 evaluable subjects per treatment group assuming 10% dropout.

- For Pain NRS, assuming a baseline mean (standard deviation [SD]) of 6.0 (1.2), follow-up mean (SD) of 3.0 (2.4) for SM04690 and 3.8 (2.4) for placebo (presumed treatment difference -0.8), and a baseline to follow-up correlation of 0.25, power is estimated to be 94.3%.
- For WOMAC Function, assuming a baseline mean (SD) of 60 (12), follow-up mean (SD) of 30 (25) for SM04690 and 37.5 (25) for placebo (presumed treatment difference -7.5), and a baseline to follow-up correlation of 0.25, power is estimated to be 89.8%.

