6.3 Safety Analysis Set

The Safety Analysis Set (SAS) includes all subjects who received a study injection. Subjects will be analyzed as treated for the SAS.

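### The common-AE table picks its rows on active-arm incidence alone, so within that table low-frequency terms tilt against active by chance; an either-arm rule would remove the tilt

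*SAP*

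**What the plan says.** SAP 10.1 lists the planned adverse event summaries. One is "AEs with incidence of greater than 2% in the active treatment group sorted by preferred term incidence". The condition refers to the active arm only. The protocol's safety analysis section (10.4.4) sets no incidence cut-off that would alter it.

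The same SAP section also plans "AEs by MedDRA system organ class and preferred term", with no incidence cut-off. Its lead sentence says that the AE tables are ones "depicting the number and percent of unique subjects experiencing each AE and the number of AEs overall and within each treatment group", so both arms are shown side by side. It adds: "Separate subject-level listings will be provided for all AEs and all SAEs".

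On the analysis set and testing, the SAP states: "The Safety Analysis Set (SAS) includes all subjects who received a study injection" (6.3) and "No formal statistical tests are planned for safety" (section 10).

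**The concern.** The table invites a comparison of two arms, but its rows are chosen on the observed result in one of them. When a term is uncommon and equally likely in both arms, it tends to enter when the active count happens to be high. The placebo count is not selected, so on average it stays at its true value. The reader then sees active above placebo more often than the underlying rates warrant. The reverse case, with placebo above 2% and active not, is absent from the table.

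Safety and tolerability are part of the study objective, and Protocol 4.2 justifies the vehicle control by the comparison it allows between the arms. With no formal safety tests planned, that comparison rests on descriptive tables. A filter that treats the arms differently is therefore worth correcting, even though the effect is confined to one table.

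**Working it through.** **Arm size.** SAP section 5 states: "A sample size of approximately 500 subjects was re-estimated for this study to yield 225 evaluable subjects per treatment group assuming 10% dropout". Check: 225 / (1 − 0.10) = 250 per arm, and 2 × 250 = 500, which agrees. Allocation is equal ("Subjects were randomized 1:1", SAP 4.2). The safety set holds everyone injected, so later dropout does not reduce it, and 250 per arm is the natural planning figure. It is a target; the SAP sections available give no safety-set count.

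**Entry rule as a count.** 5/250 is exactly 2.0%, which is not above 2%. A term therefore needs at least 6 active subjects (6/250 = 2.4%).

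**Model.** The number of active subjects with a given term is X ~ Binomial(250, p), independent of the placebo count, with the same p in both arms. The documents give no AE rates, so p is assumed and varied from 1% to 5%.

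- Chance that a term is shown: S = P(X ≥ 6).
- Expected active rate when shown: E[X | X ≥ 6] / 250 = p × P(Y ≥ 5) / S, with Y ~ Binomial(249, p).
- Expected placebo rate when shown: p, because placebo plays no part in selection.
- Chance that placebo exceeds 2% and the term is left out: S × (1 − S).

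At p = 2%: S = 0.384 and P(Y ≥ 5) = 0.558. The expected active rate is 0.02 × 0.558 / 0.384 = 2.90%, and the omission probability is 0.384 × 0.616 = 0.24.

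| Assumed true rate, both arms | Term shown | Active when shown | Placebo when shown | Ratio | Placebo above 2% and term left out |
|---|---|---|---|---|---|
| 1% | 4% | 2.59% | 1.00% | 2.59 | 4% |
| 1.5% | 18% | 2.72% | 1.50% | 1.82 | 14% |
| 2% | 38% | 2.90% | 2.00% | 1.45 | 24% |
| 3% | 76% | 3.42% | 3.00% | 1.14 | 18% |
| 4% | 94% | 4.15% | 4.00% | 1.04 | 6% |
| 5% | 99% | 5.04% | 5.00% | 1.01 | 1% |

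The last column is a joint probability over all terms at that rate, not the probability given that placebo exceeds 2%. The largest ratios belong to terms that seldom enter the table. At a true 2%, active is the higher arm in 76% of shown terms and placebo in 14%; the rest are ties.

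**Other arm sizes.** At 225 per arm (at least 5 subjects) a true 2% term shows 2.80% against 2.00%. At 363 per arm, half of the 726 in Protocol 10.5 (at least 8 subjects), it shows 2.67% against 2.00%. The direction does not depend on the sample size.

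**True differences, 250 per arm.** At a true 1% on active and 3% on placebo, the term is shown with probability 4% under the SAP rule and 77% under an either-arm rule. At 2% and 4%, the figures are 38% and 96%.

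**Either-arm rule, equal true rates.** At a true 2%, the expected display is 2.34% in both arms, and each arm is the higher one in 46.9% of shown terms.

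**The case against.** The strongest reply is that this is only a display preference. The unrestricted by-arm table and the full listings stand in the same SAP section, so every term missing from the short table is still reported. Each row shown carries the true observed counts in both arms. No safety test or decision rule uses the table. Under equal true rates the tilt runs against the study drug, so the rule does not flatter it. All of this stands, and it limits the point to a minor one.

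A reader might infer that the plan conceals events that are commoner on placebo. The documents do not support that. Only terms at or below 2% on active drop out, and only from this table; a term at 3% on active and 6% on placebo would be shown. A reader might also suppose that this will be the table quoted for tolerability, and so conclude that the safety comparison as a whole is biased. Neither document ranks the AE summaries, so that step has no basis.

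It is also fair to say that the rates are assumed, that the effect is greatest near the cut-off, and that an either-arm rule still inflates displayed rates somewhat. It does so equally in both arms, however, which is what matters for a comparison.

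**Conclusion.** The point holds in a limited form. The row-selection rule is one-sided, and within this table it tilts terms with true rates of about 1% to 3% against active by chance. The tilt is negligible by 4% to 5%. The direction follows from the rule itself; the size rests on about 250 subjects per arm, independent arms and assumed AE rates. No data are lost, and no endpoint, test or formal safety conclusion changes. It is a cheap improvement to a planned arm-comparison table, not a defect in the safety evaluation.

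**What to change.** In SAP 10.1, change the condition for this table so that a preferred term is included when its incidence exceeds 2% in either treatment group, and show both arms. A cut-off on the pooled incidence would also treat the arms alike.

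The cost is a few words, one table filter and a longer table. For scale, take an illustrative mix of 106 terms with assumed true rates of 0.5% to 5%, equal in the two arms, and 250 subjects per arm. The SAP rule shows about 12.7 terms, of which 8.3 are higher on active and 3.2 higher on placebo. The either-arm rule adds about 5.1, giving 17.8 (17.8 / 12.7 = 1.40, about 40% longer), split 8.3 and 8.3. If the SAP is not to be reopened, the either-arm table can be added to the clinical study report beside the planned one.

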10.2 Clinical Laboratory Evaluations

All chemistry, hematology and urinalysis results from the central laboratory will be summarized into shift tables as normal, non-clinically significant abnormal, and clinically significant abnormal. Assessments of clinical significance for abnormal values were made by the investigator on results that were outside of the normal range. Shift tables will compare the number and percent of assessments from each visit to baseline values for each treatment group.

All chemistry and hematology results from the central laboratory will be summarized for each treatment group. Descriptive statistics of each laboratory test at all timepoints will be provided along with the change from baseline at each subsequent visit. If a result is below the limit of quantification, it will be set to half the value for analysis (e.g., “< 3” will be analyzed as 1.5). The International System of Units (SI) will be used for all summaries.

Abnormal chemistry, hematology, urinalysis, and urine microscopy results for each subject will be provided in listings that will include laboratory test name, result, normal range, and an

explanation for clinically significant values. HbA1c values will be listed in conventional units (%).

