14. Treatment with systemic (oral, intramuscular, or intravenous) glucocorticoids \geq 10 mg prednisone or the equivalent per day within 4 weeks prior to Day 1; or subjects on $<$ 10 mg prednisone or the equivalent per day who have not maintained a stable regimen for at least 2 weeks prior to Day 1 in the opinion of the Investigator
15. Use of centrally acting analgesics (refer to [Appendix 2](#)) within 12 weeks prior to Day 1
16. Use of anticonvulsants (refer to [Appendix 2](#)) within 12 weeks prior to Day 1
17. Subjects requiring the use of opioids $>$ 1x per week within 12 weeks prior to Day 1
18. Topical local anesthetic agents (gels, creams, or patches such as the Lidoderm patch) used for the treatment of knee OA within 7 days of Day 1
19. Planned surgery scheduled during the study period, not including non-surgical invasive procedures conducted for a diagnostic or therapeutic purpose scheduled during the study period (refer to [Section 7.6](#)).
20. History of malignancy within the last 5 years, not including subjects with prior history of adequately treated in situ cervical cancer or basal or squamous cell skin cancer
21. Clinically significant abnormal screening hematology values, blood chemistry values, or urinalysis values as determined by the Investigator
22. Any condition that, in the opinion of the Investigator, constitutes a risk or contraindication for participation in the study or that could interfere with the study objectives, conduct, or evaluation
23. Other conditions that, in the opinion of the Investigator, could affect study endpoint assessments of either knee, including, but not limited to, peripheral neuropathy (e.g., diabetic neuropathy), symptomatic hip osteoarthritis, symptomatic degenerative disc disease, and patellofemoral syndrome
24. Comorbid conditions that could affect study endpoint assessments of the target knee, including, but not limited to, rheumatoid arthritis, psoriatic arthritis, systemic lupus erythematosus, gout or pseudogout, and fibromyalgia
25. History of mania, bipolar disorder, psychotic disorder, schizophrenia, or schizoaffective disorder
26. Any known active infections, including urinary tract infection, upper respiratory tract infection, sinusitis, suspicion of IA infection, hepatitis B or hepatitis C infection, and/or infections that may compromise the immune system such as human immunodeficiency virus (HIV) at Day 1

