7.2 LABORATORY PROCEDURES/EVALUATIONS

7.2.1 CLINICAL LABORATORY EVALUATIONS

Samples for clinical laboratory analysis by Medpace Central Laboratories will be collected by a qualified staff member at the Screening Visit and Weeks 4, 12, 24, and 28 (EOS)/ET. Refer to the Laboratory Manual for details about collection of specimens. At a minimum, the following tests will be conducted:

- **Chemistry panel:** Albumin, alkaline phosphatase (ALP), alanine aminotransferase (ALT), aspartate aminotransferase (AST), blood urea nitrogen, bicarbonate, calcium, calcium (corrected total), chloride, creatinine, glucose, lactate dehydrogenase (LDH), potassium, sodium, bilirubin (total)
- **Hematology:** Hemoglobin, hematocrit, red blood cell (RBC) count, white blood cell (WBC) count with differential, and platelet count
- **Urinalysis:** Clarity, specific gravity, pH, protein, glucose, ketones, nitrite, leukocyte esterase, and occult blood

An HbA1c test will be performed on all subjects at the Screening Visit.

Urine microscopy will be performed if urinalysis urine protein, leukocyte esterase (WBC esterase), occult blood, or nitrite values are out of range, or if the Investigator deems that the microscopy is clinically warranted.

The Investigator or designee must review the results of each subject's Screening Visit clinical laboratory test results prior to the Day 1 visit. The subject must not be randomized on Day 1 if any of the Screening Visit results are outside the normal range for the laboratory AND, in the opinion of the Investigator, are clinically significant.

The results of the clinical laboratory tests will be reported on the laboratory's standard reports. The Investigator must review all laboratory reports in a timely manner, noting "not clinically significant" (NCS) or comment on the clinical significance of any result that is outside the normal range for the laboratory, then date and initial the report. The Investigator must report all laboratory results that are BOTH outside the normal range for the laboratory AND, in the opinion of the Investigator, are clinically significant. If any abnormal, clinically significant laboratory measure is found prior to study medication injection, the subject is to be excluded. If it is found after study medication injection, it should be reported as an AE.

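### The laboratory shift tables merge values below and above the normal range, so no planned output counts by arm how many results moved low or high

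*SAP*

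**What the plan says.** SAP 10.2 (Clinical Laboratory Evaluations) has the central laboratory chemistry, hematology and urinalysis results "summarized into shift tables as normal, non-clinically significant abnormal, and clinically significant abnormal". On who grades them it says: "Assessments of clinical significance for abnormal values were made by the investigator on results that were outside of the normal range". On layout: "Shift tables will compare the number and percent of assessments from each visit to baseline values for each treatment group".

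The same section adds two other displays. Chemistry and hematology tests get descriptive statistics at every timepoint, with change from baseline. SAP 7.1 defines these as number of subjects, mean, SD, median, minimum and maximum, by treatment group. Abnormal results go into subject listings that show the value and its normal range.

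Protocol 7.2.1 adds a rule for a clinically significant abnormal result: "If it is found after study medication injection, it should be reported as an AE". SAP 10.1 tabulates adverse events by preferred term within each treatment group.

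Laboratory measures are a named safety endpoint (Protocol 3.2.3; SAP 3.2.3). No formal safety tests are planned (Protocol 10.4.4; SAP 10). Neither those sections nor SAP 10.2 contains a low/high split, a toxicity grade or a threshold in multiples of a normal limit.

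**The concern.** For an analyte with both a lower and an upper limit, such as potassium, sodium, calcium, glucose, white cells or platelets, a fall below range and a rise above it mean different things for safety. The planned table gives both the same label. Protocol 10.4.4 says safety will be judged partly on how laboratory parameters change relative to baseline, and with no formal tests the reader depends on the displays. A shift table is normally where one looks to see how many results left the range, in which direction, and whether the arms differ. This one answers only whether results left the range.

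**Working it through.** The SAP states no figure to reproduce here. The check is an enumeration of what the table can and cannot separate.

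**Inputs**
- Categories (SAP 10.2): normal; abnormal, not clinically significant (NCS); abnormal, clinically significant (CS). The laboratory range separates normal from abnormal. The investigator separates NCS from CS.
- Baseline (SAP 7.1.1): the last value before injection. Laboratory samples are scheduled at Screening and not on Day 1 (Protocol 7.3.7), so baseline is normally the Screening value.
- Entry rule (Protocol exclusion 21 and 7.2.1): a CS value before injection excludes the subject. Baseline can therefore be low NCS, normal or high NCS, barring an eligibility deviation.

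**Range alone.** Low, normal and high give 3 × 2 = 6 possible changes of state.
- Low to high and high to low: 2 changes, both on the diagonal if both values are NCS.
- Normal to low with normal to high, and low to normal with high to normal: 4 changes pooled into 2 cells at any one significance grade.

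**With the significance grade.** There are 3 permitted baseline states and 5 post-baseline states (low CS, low NCS, normal, high NCS, high CS), so 3 × 5 = 15 transitions. They fall into the table as follows:

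| Baseline → visit in the SAP table | Directional transitions pooled |
|---|---|
| Normal → normal | 1 |
| Normal → NCS | 2 |
| Normal → CS | 2 |
| NCS → normal | 2 |
| NCS → NCS | 4, of which 2 are low/high reversals |
| NCS → CS | 4, of which 2 are low/high reversals |
| **Total** | **15 in 6 cells** |

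Only one of the 6 cells, normal to normal, has an unambiguous direction.

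**Illustration (assumed counts, not trial data).** Suppose that, at one significance grade, active has 10 new highs and 0 new lows and placebo has 5 of each. The normal-to-abnormal cell shows 10 + 0 = 10 on active and 5 + 5 = 10 on placebo. The shift tables agree although new highs are 10 against 5. The descriptive statistics and listings could still differ between arms.

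**Other planned outputs**
- Mean and median change are signed but can hide a few opposing moves.
- Minimum and maximum change show the largest fall and rise in each arm at each visit. Each is one value; neither counts results nor shows that a limit was crossed.
- Listings give the value and range, so direction can be read, but a by-arm count would have to be made by hand.
- Adverse event tables cover results judged CS, not out-of-range results as such.

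**After the fix.** A low/normal/high table has 9 cells. Three end in normal, and six end out of range, each split by the CS count: 3 + 6 × 2 = 15, so every permitted transition can be separated.

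**The case against.** The strongest defense is that the grading follows the protocol. Its synopsis says safety is assessed through clinically significant laboratory changes as judged by the investigator, and the SAP tabulates that judgment. CS results after injection must also be reported as adverse events and so reach by-arm tables. The signed change statistics, with extremes, are given by arm for every chemistry and hematology test. All of this stands. It is a reason to keep the investigator's call beside the direction, and it narrows the gap to the missing count. The diagonal case also requires a subject to cross the whole normal range with both values judged NCS, and the documents give no frequency for that.

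A reader might infer more than the documents support:
- *That direction is lost from the plan.* It is lost from the shift tables only, as the other outputs show.
- *That the whole grading is opinion.* The laboratory range sets normal against abnormal; only NCS against CS is judgment. The Protocol and SAP give no numerical criterion for it, and it is made at about 100 sites. Assessments after injection are restricted to blinded personnel (Protocol 6.1.5 and 10.6.1), so variation between sites should add noise rather than favor an arm.
- *That the CS baseline row is a defect.* Protocol 7.2.1 says "If any abnormal, clinically significant laboratory measure is found prior to study medication injection, the subject is to be excluded", so 3 of the 9 cells should be empty. An empty row biases nothing and would expose an eligibility deviation. It would also remain for urinalysis under the fix below.

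**Conclusion.** The point holds as a limited one about safety reporting. The SAP 10.2 shift tables cannot distinguish new lows from new highs, and no planned output supplies that count by arm. For an analyte with limits on both sides, 15 permitted transitions appear as 6. This assumes that the Screening sample is the baseline and that no subject enters with a CS value. For an analyte where only one direction can occur or matters, little or nothing is lost. How often the merging would hide a difference between arms cannot be estimated from the documents. The primary and secondary efficacy analyses, alpha and sample size do not change, and nothing here contradicts the protocol. It is a worthwhile improvement rather than a necessary correction.

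**What to change.** In SAP 10.2, for chemistry and hematology, present shift tables of low, normal and high from the central laboratory range, by visit and treatment group. Beside each out-of-range direction, show how many results the investigator judged clinically significant. Keep the current grading for urinalysis.

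The value and normal range are already required for the listings, so the categories can be derived without new data, visits or a protocol amendment. The cost is extra table programming. Because the SAP is already signed, it also needs either a revised version or a note in the study report that the tables were added.
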